**CONFIDENTIAL**

201214

2.8.	Efficacy	Non-standard EFF_T1	Summary Table of Change from Baseline in TTP Counts Over Time	Include baseline row similar to LB1 template.	SAC
2.9.	Efficacy	Non-standard EFF_T2	Rate of Change in TTP –Mixed Model Analysis	Supportive SAS output to be produced and archived	SAC
2.10.	Efficacy	Non-standard EFF_T3	Node and Slope Parameter Estimates for TTP by Treatment –Bi-linear Bayesian Model Analysis	For endpoint TTP(0-14) only. Supportive SAS output to be produced and archived	

## 12.10.6. Efficacy Figures

Efficacy: Figures					
No.	Population	IDSL / Example Shell	Title	Programming Notes	Deliverable
Efficacy					
2.1.	Efficacy	Non-standard EFF_F1	Line Graph of log 10 CFU Over Time by Treatment	Include separate lines for each dose/treatment group.	DE, SAC
2.2.	Efficacy	Non-standard EFF_F1	Line Graph of Change from Baseline in log 10 CFU Over Time by Treatment	Include separate lines for each dose/treatment group.	DE, SAC
2.3.	Efficacy	Non-standard EFF_F2	Individual Subject Profile Plots of log 10 (CFU) Count Over Time by Treatment	Include CFU(0-14) regression line and 95% CI. Separate figure for each treatment group.	SAC
2.4.	Efficacy	Non-standard EFF_F3	Line Graph of Dose vs log 10 CFU (0-14) Slope	Include regression line and 95% CI	DE, SAC
2.5.	Efficacy	Non-standard EFF_F1	Line Graph of TTP Over Time by Treatment	Include separate lines for each dose/treatment group.	SAC

## 12.10.7. Safety Tables

Safety: Tables					
No.	Population	IDSL / Example Shell	Title	Programming Notes	Deliverable
Adverse Events (AEs)					
3.1.	Safety	AE5B	Summary of All Adverse Events by System Organ Class, Preferred Term and Maximum Grade	ICH E3	SAC
3.2.	Safety	AE5B	Summary of All Drug-Related Adverse Events by System Organ Class, Preferred Term and Maximum Grade	ICH E3	SAC
3.3.	Safety	AE15	Summary of Common (>=5%) Non-serious Adverse Events by System Organ Class and Preferred Term (Number of Subjects and Occurrences)	FDAAA, EudraCT	SAC
Serious and Other Significant Adverse Events					
3.4.	Safety	AE16	Summary of Serious Adverse Events by System Organ Class and Preferred Term (Number of Subjects and Occurrences)	FDAAA, EudraCT	SAC
3.5.	Safety	AE5B	Summary of Adverse Events Leading to Permanent Discontinuation of Study Treatment by System Organ Class, Preferred Term and Maximum Grade	IDSL	SAC
3.6.	Safety	AE5B	Summary of Adverse Events Leading to Withdrawal from Study by System Organ Class, Preferred Term and Maximum Grade	IDSL	SAC
3.7.	Safety	AE20	Summary of Serious Fatal and Non-Fatal Drug-Related Adverse Events by Overall Frequency	Plain Language Summary requirements (PLS).	SAC
3.8.	Safety	PAN10	Summary of Exposure Adjusted Incidence Rates of Adverse Events Over Time Relative to COVID-19 Pandemic Measures		SAC
3.9.	Safety	PAN10	Summary of Exposure Adjusted Incidence Rates of Adverse Events Over Time By Age Relative to COVID-19 Pandemic Measures		SAC

Safety: Tables					
No.	Population	IDSL / Example Shell	Title	Programming Notes	Deliverable
Laboratory: Chemistry					
3.10.	Safety	LB1	Summary of Chemistry Changes from Baseline	ICH E3	SAC
3.11.	Safety	LB17	Summary of Worst Case Chemistry Results by PCI Criteria Post-Baseline Relative to Baseline	ICH E3	SAC
Laboratory: Haematology					
3.12.	Safety	LB1	Summary of Haematology Changes from Baseline	ICH E3	SAC
3.13.	Safety	LB17	Summary of Worst Case Haematology by PCI Criteria Post-Baseline Relative to Baseline	ICH E3	SAC
Laboratory: Urinalysis					
3.14.	Safety	UR1	Summary of Worst Case Urinalysis Results Post-Baseline Relative to Baseline	ICH E3	SAC
Laboratory: Hepatobiliary (Liver)					
3.15.	Safety	LIVER1	Summary of Liver Monitoring/Stopping Event Reporting	IDSL	SAC
3.16.	Safety	LIVER10	Summary of Hepatobiliary Laboratory Abnormalities	IDSL	SAC
ECG					
3.17.	Safety	EG1	Summary of ECG Findings	IDSL	SAC
3.18.	Safety	EG10	Summary of Maximum QTc Values Post-Baseline Relative to Baseline by Category	IDSL	SAC
3.19.	Safety	EG2	Summary of Change from Baseline in ECG Values by Visit	IDSL	SAC
3.20.	Safety	EG11	Summary of Maximum Increase in QTc Values Post-Baseline Relative to Baseline by Category	IDSL	SAC
Vital Signs					
3.21.	Safety	VS1	Summary of Change from Baseline in Vital Signs	ICH E3	SAC

Safety: Tables					
No.	Population	IDSL / Example Shell	Title	Programming Notes	Deliverable
3.22.	Safety	VS7	Summary of Worst Case Vital Signs Results by PCI Criteria Post-Baseline Relative to Baseline	IDSL	SAC
COVID-19 Assessments					
3.23.	Safety	PAN1	Summary of COVID-19 Assessments for Subjects with COVID-19 Adverse Events		SAC

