### 5.1. Overall Design

The study will comprise up to 5 cohorts of participants. It is intended that 9-15 participants in each cohort (dependent on the cohort) will receive GSK3036656 and 3-5 will receive standard-of-care regimen for DS-TB (i.e. Rifafour e-275 or equivalent generic alternative), with a randomisation ratio of 3:1. There will be no placebo in this study. The study will be randomized, but not blinded (i.e., it will be ‘open-label’) with neither participant nor Investigator blinded to treatment. Study participants will revert to the standard treatment for TB (i.e. Rifafour e-275 or equivalent generic alternative) once the study treatment (Day 1 to Day 14) has been completed. All laboratory staff involved in analysing and reporting the primary and secondary change in log10CFU counts and TTP endpoints results will be blinded to treatment allocation. Cohorts will proceed sequentially starting A through E, with preliminary safety, tolerability and pharmacokinetic data from the previous cohort reviewed prior to selecting the dose for the next cohort.

[figure not shown]
It is anticipated that it may be necessary to administer a dose of GSK3036656 the same or lower than in a previous cohort, dependent on preliminary safety, tolerability, pharmacokinetic or efficacy data.

CCI [REDACTED]

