### 13.7. Appendix 7: Liver Safety: Required Actions and Follow-up Assessments

#### Liver chemistry stopping criteria and required follow up assessments

Elevated liver enzymes, transient liver dysfunction, hepatotoxicity and hepatitis are listed as side-effects in the package inserts for Rifafour e-275 (Rifafour, 2002) or equivalent generic alternative, associated with multiple drug components. Therefore, participants allocated to Rifafour e-275 (or equivalent generic alternative) treatment who experience Liver Chemistry Stopping criteria are not mandated in the first instance to undergo those follow-up assessments (which are intended to investigate aetiology). The investigations may still be performed, if required in the judgement of the investigator.

Liver Chemistry Stopping Criteria	
ALT-absolute	ALT $\geq$ 5xULN
ALT Increase	ALT $\geq$ 3xULN persists for $\geq$ 4 weeks
Bilirubin	ALT $\geq$ 3xULN and bilirubin $\geq$ 2xULN (>35% direct bilirubin)
INR^2	ALT $\geq$ 3xULN and INR>1.5, if INR measured
Cannot Monitor	ALT $\geq$ 3xULN and cannot be monitored weekly for 4 weeks
Symptomatic	ALT $\geq$ 3xULN associated with symptoms (new or worsening) believed to be related to liver injury or hypersensitivity
Required Actions and Follow up Assessments	
Actions	Follow Up Assessments

 
• Immediately discontinue study treatment
 
• Report the event to GSK within 24 hours
 
• Complete the liver event CRF and complete an SAE data collection tool if the event also meets the criteria for an SAE
 
• Perform liver chemistry event follow up assessments
 
• Monitor the participant until liver chemistries resolve, stabilize, or return to within baseline (see MONITORING below)
 
• Do not restart/rechallenge participant with study treatment unless allowed per protocol
 
	
For all study participants:
 
 
• Obtain INR and recheck with each liver chemistry assessment until the transaminases values show downward trend
 
• Record the appearance or worsening of clinical symptoms of liver injury, or hypersensitivity, on the AE report form
 
• Record use of concomitant medications on the concomitant medications report form including acetaminophen, herbal remedies, other over the counter medications.
 

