### 2.3. Study Design

Overview of Study Design and Key Features	
<pre> graph LR     A[SCREENING from -9 days prior to first dose] --> B[14-Day treatment period - GSK3036656]     A --> C[14-Day treatment period - Rifafour]     B --> D[Day 15 start/continue Rifafour*]     C --> D     D --> E[Follow-up at Day 28]             </pre> 
*This is not part of the study but is the post-study definitive treatment of TB.
	
Design Features	
 
• A single-centre, open-label trial in up to five sequential cohorts.
 
• Each cohort will involve participants being randomised to one of two possible treatments: either GSK3036656 or Standard-of-Care (SoC) regimen (e.g. Rifafour®e-275) for rifampicin-susceptible (drug sensitive) tuberculosis (DS-TB).
 
• Screening will be performed on days -9 to -1, followed by 14 days of once daily dosing and a follow-up visit 28 days after the first dose.
 
• All laboratory staff involved in analysing and reporting the primary and secondary change in CFU counts and TTP endpoint results will be blinded to treatment allocation.
 

Dosing	
 
• Once daily repeat dosing for 14 days.
 
• The starting dose for the GSK3036656 arm is a 15mg loading dose on Day 1 and 5mg maintenance dose on Days 2-14, given orally. The study will employ dose escalation, where the GSK3036656 dose for each cohort will be decided based on reviews of preliminary safety, tolerability and pharmacokinetic data; in addition, efficacy data will be considered if available.
 

Time & Events	
 
• See Appendix 2: Schedule of Activities
 

Treatment Assignment	
 
• 12-20 participants in each cohort (excluding possible replacements), randomised 3:1 to GSK3036656 or Standard of Care respectively.
 
• GSK RandAll NG will be used to generate the randomisation schedule.
 

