## 12.4. Appendix 4: Study Phases and Treatment Emergent Adverse Events

### 12.4.1. Study Phases

Adverse events will be classified according to the time of occurrence relative to the start of study treatment.

Study Phase	Definition
Pre-Treatment	Date and Time $\leq$ Study Treatment Start Date and Time
On-Treatment	Study Treatment Start Date and Time $<$ Date and Time $\leq$ Study Treatment Stop Date and Time + 48 hours
Post-Treatment	Date and Time $>$ Study Treatment Stop Date and Time + 48 hours

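### Worst-case safety displays count Day 28 values taken on Rifafour within the GSK3036656 dose groups, and no adverse event table is tied to the SAP's own treatment phases

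*SAP*

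**What the plan says.** **The switch.** Protocol 5.1 states: "Study participants will revert to the standard treatment for TB (i.e. Rifafour e-275 or equivalent generic alternative) once the study treatment" has been completed. The schematic in SAP 2.3 dates this for both arms as "Day 15 start/continue Rifafour", so GSK3036656 participants start Rifafour and SoC participants stay on it. The footnote there adds: "This is not part of the study but is the post-study definitive treatment of TB". Under Protocol Section 8, a participant who stops investigational product may be placed on standard of care sooner and remain in the study.

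**Collection.** In the schedule of activities, adverse events run from first dose to the Day 28 visit. Chemistry, haematology, urinalysis, ECG and vital signs are also taken then. SAP 12.3.1 windows Day 21 to Day 35 as a safety timepoint.

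**Laboratory, ECG and vital sign displays.** Table 3.11 is titled "Summary of Worst Case Chemistry Results by PCI Criteria Post-Baseline Relative to Baseline". Tables 3.13, 3.14, 3.18, 3.20 and 3.22 likewise take a worst or maximum value after baseline, and Table 3.16 states no time limit. SAP 12.6.1 refers to a row covering any post-baseline visit. Figure 3.1 (ALT against bilirubin, by treatment) is to include all timepoints, and Figure 3.2 plots the maxima. Protocol 10.3.2 reports worst-case results by dose group.

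**Adverse event displays.** SAP 12.4.1 says: "Adverse events will be classified according to the time of occurrence relative to the start of study treatment". It defines On-Treatment as running to treatment stop plus 48 hours and Post-Treatment as anything later. SAP 12.4.2 defines a matching treatment-emergent flag. Table 3.1 is titled "Summary of All Adverse Events by System Organ Class, Preferred Term and Maximum Grade". Neither SAP 8.1 nor any title or programming note for Tables 3.1 to 3.7 mentions a phase or the flag. Tables 3.8 and 3.9 split by pandemic period only.

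**The concern.** The safety objective concerns GSK3036656 given once daily for 14 days. A table headed by a GSK3036656 dose but filled with values up to Day 28 describes 14 days of that drug followed by about two weeks of a four-drug regimen.

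For liver chemistry the protocol supplies the mechanism. Appendix 7 states: "Elevated liver enzymes, transient liver dysfunction, hepatotoxicity and hepatitis are listed as side-effects in the package inserts for Rifafour e-275". An ALT rise first seen at Day 28 would appear as the worst-case result of a GSK3036656 dose group. A worst-case table discards the date, so its reader cannot tell.

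The switch introduces a new drug in the GSK3036656 columns only. It therefore adds a source of events that does not depend on GSK3036656 dose, and with groups as small as nine a single participant visibly moves a percentage.

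**Working it through.** The plan states no figure on this point, so there is nothing to reproduce. The check sets the passages side by side and then sizes the exposure.

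**1. Which data have a phase rule?**

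| Data | Phase defined in SAP 12.4? | Used in 12.10.7? | End date in display? |
|---|---|---|---|
| Adverse events, Tables 3.1 to 3.7 | Yes | No | None stated |
| Worst-case or maximum laboratory, ECG and vital signs: 3.11, 3.13, 3.14, 3.18, 3.20, 3.22 | No | Not applicable | None stated |
| Hepatobiliary: 3.16, Figures 3.1 and 3.2 | No | Not applicable | None stated; Figure 3.1 takes all timepoints |
| By-visit tables: 3.10, 3.12, 3.19, 3.21 | Not needed | Not applicable | Day 28 is a separate timepoint |

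**2. Which adverse event tables can be affected?** Tables 3.1, 3.3, 3.4 and 3.6 can. Table 3.5 (discontinuation of study treatment) cannot, because Rifafour started after study treatment ended cannot have caused it to stop. Tables 3.2 and 3.7 hold only drug-related events, so they are affected only through misattribution.

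**3. Share of the collection period after the switch.** For a completer with last dose on Day 14 and follow-up on day v, days after the switch = v − 14. Days after the SAP's On-Treatment window = v − 16.

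| v | (v − 14)/v | (v − 16)/v |
|---|---|---|
| 21 | 7/21 = 33% | 5/21 = 24% |
| 28 | 14/28 = 50% | 12/28 = 43% |
| 35 | 21/35 = 60% | 19/35 = 54% |

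These are shares of calendar time, not estimates of bias.

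**4. Weight of one participant.** Protocol 10.1.2 reduces ongoing and future cohorts to 9 per GSK3036656 arm, from 15. One participant is 1/9 = 11.1 points, or 1/15 = 6.7 points.

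**5. Chance of at least one such participant.** The documents give no rate of Rifafour-caused abnormality, so p is an assumption. P(at least one) = 1 − (1 − p)^n.

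| Assumed p | n = 9 | n = 15 |
|---|---|---|
| 2% | 17% | 26% |
| 5% | 37% | 54% |
| 10% | 61% | 79% |

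**6. Exposure-adjusted rates, Tables 3.8 and 3.9.** SAP 12.6.2 defines exposure as study-drug days, 14 for a completer, but the denominator for these tables is not stated. If it is 14 days while events count to day v, a constant background rate is overstated by v/14: 21/14 = 1.5, 28/14 = 2.0, 35/14 = 2.5.

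**7. Would a cut at Day 15 isolate Rifafour?** Protocol 5.6 gives a GSK3036656 half-life of 45 hours. Assuming simple exponential decline, 0.5^(48/45) = 48% of drug remains 48 hours after the last dose. Five half-lives are 5 × 45/24 = 9.4 days. The period after the switch is therefore mixed.

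**The case against.** The strongest reply has four parts.

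- **The phases must be meant for use.** SAP 12.4 says events will be classified, and 12.7.2.1 assigns adverse events with missing dates to the on-treatment period for reporting. These rules are pointless unless the tables use them. The displays follow GSK standard shells that are not in the documents and may apply a phase. This stands in part: a reader might infer that the adverse event tables certainly mix the periods, but the documents show only that their scope is not stated. It does not help the laboratory displays, for which no treatment phase is defined.
- **An all-event table is what the protocol asks for.** Protocol 10.3.2 lists its separate summaries in addition to all adverse events. This stands, and is a reason to add a split rather than restrict Table 3.1.
- **Dropping Day 28 would lose signal.** Protocol 3.3.1 reports a first-in-human haemoglobin trend measured from baseline to follow-up, and one low neutrophil count seen only at follow-up. This stands. It would be wrong to infer that late events are all Rifafour effects or that tables should stop at Day 15.
- **Timing is traceable elsewhere.** By-visit tables, individual ALT and haematology profiles (Figures 3.3 and 3.4) and listings allow a Day 28 rise to be found. The analysis is descriptive, and the safety tables belong to the final deliverable only. This limits the harm, but the dose-group counts remain uninterpretable without that search.

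**Conclusion.** The point holds as a gap in the display specification. It is firm for the worst-case, maximum and hepatobiliary displays: followed as written, they place Day 28 values obtained on Rifafour in GSK3036656 dose-group counts. It matters most for Tables 3.11 and 3.16 and Figures 3.1 and 3.2, because liver effects are the only Rifafour effects in these displays that the protocol names. For adverse events the finding is narrower: suitable definitions exist, and no table is linked to them.

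The size is 50% of the collection period for a completer seen on Day 28 (33% to 60% across the visit window), and 11.1 points per affected participant in a group of nine. The overstatement of rates in Tables 3.8 and 3.9 and the chances in step 5 depend on assumptions the documents do not settle.

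Two further inferences are unsupported. A reader might suppose that every participant changes drug, but the SoC arm does not. A reader might also suppose that the contrast with SoC must shrink. Extra events in the GSK3036656 columns narrow it if SoC has the higher incidence and widen it if GSK3036656 does.

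**What to change.** Keep every overall row and add a split.

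- **Adverse events.** In Tables 3.1, 3.3, 3.4 and 3.6, add on-treatment and post-treatment blocks using the SAP 12.4 definitions. In the GSK3036656 columns, label the second block as after the start of Rifafour. This is optional for 3.2 and 3.7 and not needed for 3.5. Footnote that the 48-hour extension overlaps the first day or two of Rifafour.
- **Worst-case, maximum and hepatobiliary displays** (Tables 3.11, 3.13, 3.14, 3.16, 3.18, 3.20, 3.22; Figures 3.1 and 3.2). Keep the any-post-baseline row. Show values up to Day 15 or early withdrawal separately from Day 28 values.
- **Participants placed on SoC early.** Start the post-switch period at the first Rifafour dose, and say that this overrides the 48-hour rule for them. Protocol 7.5 requires dates for any medication received during the study, so the date should be available.
- **Tables 3.8 and 3.9.** State an exposure denominator that covers the same period as the events counted.
- **Footnote to all split displays.** State that the post-switch block contains residual GSK3036656 exposure and is not attributed to either drug.

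The cost is SAP wording, extra programming and longer tables. No new data are collected and nothing is removed from view. The remaining weakness is that a split by date cannot separate a delayed GSK3036656 effect from a Rifafour effect.

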12.10.8. Safety Figures

Safety: Figures					
No.	Population	IDSL / Example Shell	Title	Programming Notes	Deliverable
Laboratory					
3.1.	Safety	LIVER9	Scatterplot of ALT vs Total Bilirubin by Treatment	Separate plots for each treatment group. Include all timepoints.	SAC
3.2.	Safety	LIVER9	Scatter Plot of Maximum ALT vs. Maximum Total Bilirubin by Treatment	IDSL Separate plots for each treatment group.	SAC
3.3.	Safety	LB11	ALT Profile Plots by Treatment	Separate plots for each treatment group, with individual lines for each subject	SAC
3.4.	Safety	LB11	Haematology Profile Plots by Treatment	Separate plots for each treatment group, with individual lines for each subject.	SAC
Vital Signs					
3.5.	Safety	LB11	Vital Signs Profile Plots by Treatment	Separate plots for each treatment group and vital signs parameter (DBP, SBP, mean BP, heart rate). Display individual lines for each subject, within a treatment, for each plot.	SAC

**12.10.9. Pharmacokinetic Tables**

Pharmacokinetic: Tables					
No.	Population	IDSL / Example Shell	Title	Programming Notes	Deliverable
Pharmacokinetic Concentration Data					
4.1.	PK	PK01	Summary of Plasma GSK3036656 Pharmacokinetic Concentration-Time Data		SAC
Derived Pharmacokinetic Parameters					
4.2.	PK	PK03	Summary of Derived Plasma GSK3036656 Pharmacokinetic Parameters (Untransformed Data)	AUC(0-t), AUC(0-24), C max , t max , C T	SAC
4.3.	PK	PK05	Summary of Derived Plasma GSK3036656 Pharmacokinetic Parameters (Log-transformed Data)	AUC(0-t), AUC(0-24), C max , t max , C T	SAC
4.4.	PK	Non-standard PK_T1	Statistical Analysis of Log Transformed Plasma GSK3036656 Pharmacokinetic Parameters Assessing Dose Proportionality (Power Model)	AUC(0-t) or AUC(0-24), C max Supportive SAS output to be produced and archived.	SAC
4.5.	PK	Non-standard PK_T2	Statistical Analysis of Log Transformed Plasma GSK3036656 Trough Concentration Assessing Steady-State	C T Supportive SAS output to be produced and archived.	SAC

## 12.10.10. Pharmacokinetic Figures

Pharmacokinetic: Figures					
No.	Population	IDSL / Example Shell	Title	Programming Notes	Deliverable
Pharmacokinetic Concentration Data					
4.1.	PK	PK16a	Individual Plasma GSK3036656 Concentration-Time Plot (Linear and Semi-Log) by Subject		SAC
4.2.	PK	PK24	Individual Plasma GSK3036656 Concentration-Time Plot (Linear and Semi-Log) by Treatment	Include Day 14 and 15 data only.	SAC
4.3.	PK	PK17	Mean Plasma GSK3036656 Concentration-Time Plots (Linear and Semi-Log)	Include Day 14 and 15 data only.	SAC
4.4.	PK	PK18	Median Plasma GSK3036656 Concentration-Time Plots (Linear and Semi-Log)	Include Day 14 and 15 data only.	SAC
Derived Pharmacokinetic Parameters					
4.5.	PK	PK25	Comparative Plot of Individual Subject Plasma GSK3036656 Pharmacokinetic Parameter By Treatment	Ct	SAC
4.6.	PK	Non-standard PK_F1	Scatterplot of log(dose) vs log(AUC)	Add footnote: Doses displayed on the log scale are Xmg, Xmg, Xmg and Xmg.	SAC
4.7.	PK	Non-standard PK_F1	Scatterplot of log(dose) vs log(Cmax)	Add footnote: Doses displayed on the log scale are Xmg, Xmg, Xmg and Xmg.	SAC

## 12.10.11. ICH Listings

ICH: Listings					
No.	Population	IDSL / Example Shell	Title	Programming Notes	Deliverable
Subject Disposition					
1.	Screened	ES7	Listing of Reasons for Screen Failure	Journal Guidelines	SAC
2.	Safety	ES2	Listing of Reasons for Study Withdrawal	ICH E3	SAC
3.	Safety	SD2	Listing of Reasons for Study Treatment Discontinuation	ICH E3	SAC
4.	Randomised	TA1	Listing of Planned and Actual Treatments	IDSL	SAC
Protocol Deviations					
5.	Safety	DV2	Listing of Important Protocol Deviations	ICH E3	SAC
6.	Safety	IE3	Listing of Subjects with Inclusion/Exclusion Criteria Deviations	ICH E3	SAC
Populations Analysed					
7.	Safety	SP3	Listing of Subjects Excluded from Any Population	ICH E3	SAC
Demographic and Baseline Characteristics					
8.	Safety	DM2	Listing of Demographic Characteristics	ICH E3 Include BMI and smoking status.	SAC
9.	Safety	DM9	Listing of Race	ICH E3	SAC
Prior and Concomitant Medications					
10.	Safety	CP_CM3	Listing of Concomitant Medications	IDSL	SAC
Exposure and Treatment Compliance					
11.	Safety	EX3	Listing of Exposure Data	ICH E3	SAC
Adverse Events					
12.	Safety	AE8CP	Listing of All Adverse Events	ICH E3	SAC

